3.2 Prevalence of Disease/Condition (Background)

In recent years researchers have investigated the prevalence of HS in the general population. However, it is difficult to get an accurate estimate of the true prevalence of HS as such studies have used different methodologies and sample sizes for estimation. In general, three types of studies have been used to estimate the prevalence: (i) registry-based studies (RBS), (ii) prospective examination of subjects (PEP), and (iii) self-reported data from larger groups (SRS). These different designs each have their strengths and weaknesses. However, the most reliable prevalence estimates come from cross-sectional, general SRS using validated screening questions and/or clinical assessment [13].

At the lower end of the HS prevalence range, most RBS from the USA estimate HS prevalence to be 0.05%–0.20%. However, Jemec and Kimball (2015) argue that these studies underestimate the true prevalence of HS as they mainly used RBS methods. RBS methods rely on a sequence of events: the subject must present for treatment, be given a correct diagnosis, and be coded appropriately. Such methods consistently give the lowest prevalence estimates. Furthermore, as the condition is frequently misdiagnosed, and the average diagnostic delay is ~ 7 years [14], there may be many undiagnosed people with HS who were excluded from these studies. It is noteworthy that some of the more recent RBS [15] that used large sample sizes estimate HS prevalence to be ~1% of the general population.

PEPs involve examination of specific groups. Such group-based studies are attractive in that they are highly specific but are limited in the numbers of subjects involved in such studies are typically small restricting the statistical significance of the data generated. The exact diagnostic criteria used in these studies have not been specified [16].

SRS are thought to offer the highest sensitivity in prevalence studies and have produced consistent results. A French SRS indicated that the prevalence of HS may be ~1% of the general population [17]. Several more recent population-based studies involving cross-sectional, general SRS using validated screening questions and/or clinical assessment estimate the prevalence of HS in Australian, Brazilian, and European populations to be ~1% [18,19,20,21]. Jemec and Kimball (2015) argue that more SRS are needed to gain an accurate picture of the true prevalence of HS.

There is significant variation in figures examining the prevalence of HS in different populations. Most European-based studies estimate the prevalence to be ~1% of the general population, while several USA and other countries using RBS estimate HS prevalence to be 0.05%–0.20%. The large variation (~250-fold) may be due to different methodologies used by researchers in estimating HS prevalence but may also reflect differences in the respective populations. There is a growing body of evidence to support the 1% figure estimated using SRS and some RBS.

3.3 Impact of Disease/Condition

HS has a massively under recognized impact on the subject's quality of life, limiting them from socialising, working, exercising and intimacy.

HS subjects see up to 5 clinicians and attend 17 appointments over the course of 8 years before a correct diagnosis is made.[2]. Many subjects live with chronic pain, become sedentary, obese and have a high risk of developing anxiety and depression. HS subjects miss an average of 3 days per

CE-GAX001-01

CR: 144

V4.0

month from work, with many losing the confidence and ability to sustain full time employment as a result. [4]

Current HS treatments include topical, pharmaceutical and surgical intervention. However, the cause of the disease remains unknown, and none of the treatment pathways offered to subjects lead to successful healing. There is no clinical standard for the every-day care of HS wounds in the home setting, yet subjects are left to deal with these life altering lesions with little direction from healthcare professionals.

While the prevalence of HS may approach that of Psoriasis, quality of life scores indicate that subjects with moderate to severe HS are substantially worse off than subjects with moderate to severe Psoriasis. These parallels are worth considering given the cost of the impact of Psoriasis is estimated to be \$35.2 billion annually in the United States [22]. High drug costs and cost settings, such as emergency department and in subject care are used more frequently for subjects with HS than other dermatological disease. Further, HS is widely misdiagnosed due to lack of awareness among the general practitioner and general population. This results in many wasted resources in the diagnosis of the condition.

3.4 Clinical Evaluation

This pilot study will evaluate usability - the safety, efficacy and performance of HidraWear AX in the home setting. Quality of life, ease of use and comfort of Hidrawear AX will be assessed.

The clinical effect of the wound pad will not be assessed. HldraWear AX does not claim wound healing but is a quicker and easier way to dress wounds.

CE-GAX001-01

V4.0

CR: 144

4 RISKS AND BENEFITS

4.1.1 Risk Analysis

- Hidradenitis Suppurativa wounds can sometimes be colonised by non-pathogenic bacteria, and may appear to be infected. This is not a true infection. However, subjects will examined by research nurse to assess the wound and will be asked to record their temperature during the study to monitor for signs of infection. There will be a registered nurse overseeing all subject interactions and demonstrations to ensure the safety of subjects
- Garment could cause discomfort to the subject. In the case of any discomfort the subject is requested to remove the wound care product
- There is also a minor concern re allergies to certain materials and this will be included in the PIL and will be an exclusion criteria

Risk assessment for Hidramed vs Standard Adhesive dressing.

Risk level and likelihood rated 1-5, 1 being the lowest and 5 being the highest.

Hidrawear AX Garment

Risk	Cause	Level of Risk	Likelihood of Risk	Control
Skin Irritation	Allergic to garment	1	1	Discontinue use immediately
Unnecessary Pain	Difficult dressing site			Use product as instructed exactly.
				Discontinue use immediately
Subject distress and embarrassment	Dressing leaking or falling off.	1	1	Use product as instructed exactly
Physical contamination of wound	Thread or fibres from product retained in wound	1	1	Selected bonded fabric that does not fray/produce fibres.
				Users instructed to carry out daily visual inspection of wound.
				Discontinue use immediately

CE-GAX001-01

V4.0

CR: 144

Dressing Supplied During Study

Risk	Cause	Level of Risk	Likelihood of Risk	Control
Skin Irritation	Allergic to dressings	1	1	Discontinue use immediately
Localised infection	Misuse of dressings	3	1	Follow user instructions exactly. Discontinue use immediately
Septicemia	Misuse of dressings	5	1	Follow user instructions exactly. Discontinue use immediately
				Monitor temperature twice daily during pilot period.
Subject distress and embarrassment	Dressing leaking or falling off.	1	1	Use product as instructed exactly

Standard Adhesive Dressing

Risk	Cause	Level of Risk	Likelihood of risk	Control
Skin Irritation	Allergic to or reaction to adhesive in dressing	1	3	Discontinue Use immediately
Localised infection	Misuse of dressings	3	3	N/A user instructions do not specify
Septicemia	Misuse of dressings	5	1	N/A user instructions do not specify
Unnecessary pain	Difficult dressing site, Adhesive damage to skin	5	4	N/A
Subject distress and embarrassment	Dressing leaking or falling off. Ineffective product for use on Armpit (sweaty, moist, mobile area of body)	3	5	N/A
Physical contamination of wound	Thread or fibres from product retained in wound	1	1	N/A

CE-GAX001-01

V4.0

CR: 144

4.2 Anticipated Clinical Benefits

- Participating in the study may give subjects a sense of control and empowerment to be involved in the evolution of a product developed for their specific needs.
- The product may provide a superior method of applying, retaining and changing a wound dressing, providing comfort and security to subjects
- Subjects may see a reduction in dressing related pain
- Subjects will get to interact daily with researcher and share their experiences of living with HS

4.3 Adverse Device Effects

Materials selected are designed for contact with the skin and all use of adhesives on the skin have been removed so the likelihood of adverse effects due to using the device is low. However, there is a slight possibility of skin irritation, infection and pain due to misuse of the device. See table in section 4.1.1

In all instances of adverse effects, subjects must cease using the device immediately and make contact with research nurse for further instruction.

4.4 Risks Associated with Participation in the Clinical Investigation

On Day 0, the subject will be asked to demonstrate or explain dressing their axilla using their usual methods and products. These products may use adhesives and in turn cause discomfort to subjects during demonstration.

4.5 Possible Interactions with Concomitant Medical Treatments

None expected as this is an assessment of the HidraWear AX garment.

4.6 Steps to be Taken to Control or Mitigate Risks

Users will be assessed by a Research Team member to establish that no infection is present in the wound site on enrolment and assessment.

Subjects will be asked to measure and record their temperature daily and to contact nurse support if there is an elevation in temperature.

If subjects record a pyrexia greater than 38 degrees. The Subject will contact the Research team where it will be recorded. Subject will be asked to recheck temperature following 1 hour without temperature reducing medication (paracetamol ibuprofen et). If pyrexia persists, subject will be directed to attend GP for immediate follow up and the use of the study device will be stopped.

Research nurse to assess whether pyrexia is device related.

If it is not device related, a telephone contact log is to be filled in and reported to the sponsor.

[figure not shown]
If it is device related, an adverse is to be recorded and reported to sponsor

CE-GAX001-01

V4.0

CR: 144

Process Flow for Pyrexia >38 Degrees

The dressing used in this study is provided sterile.

The fastener used in this study is used externally and does not touch the skin during use. Material base and Velcro is medical grade.

The dressing and fastener will be CE marked by the legal manufacturer (Planet Medical Products Co. Ltd., China). The manufacturer is ISO13485 certified.

Hidramed AX fabric is an OEKO-TEX® certified material. The Hidramed AX full produced garment has been evaluated in accordance with ISO 10993 and it is biocompatible for its intended use. Verification and validation testing will be performed to evaluate the design of the garment. Hidramed Solutions will CE mark the device in accordance with the medical device directive 93/42/EEC.

CE-GAX001-01

V4.0

CR: 144

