6.1.4 Methodology

Before the study commences on site, a survey will be shared into select closed patient groups online, to capture the patient experience of living with Hidradenitis Suppurativa (HS) in terms of self-managing wound care and the impact that HS wound care has on patients' day to day life, physically, financially and emotionally.

A secure and confidential survey tool (Typeform) will be used. This is governed under EU data legislation and encrypted to ensure privacy. The survey will not collect any identifying information and is a precursor to the HidraWear AX Pilot Study.

Day 0

Subjects will visit trial site or have a home visit from research nurse.

Following consent and enrolment, Subjects will be asked to demonstrate or explain their usual method of dressing their wound using their usual wound dressing products.

Subjects will assess this activity based on ease of use, comfort, experienced pain, confidence in dressing retention and time, using a 10 point visual analogue scale. (see appendix 2)

The subjects will complete a Dermatology Quality of Life Index Survey. (see appendix 5)

The research nurse will assess the activity based on whether the subject needs assistance, uses additional equipment, contorts or stretches their body, can dress the wound without raising their arms above their head. (See appendix 4)

Day 1-21

Daily Check in with Subjects:

Each day, at 1pm, subjects will receive an email requesting them to check in with the researcher by answering 3 questions.

- 1. What is your temperature?
- 2. How many dressings did you use in the last 24 hours?
- 3. Any comments?

This check in should take less than 5 minutes to complete.

Subjects will be required to respond by 5pm each evening. If subject has not responded by 5pm, a reminder text message will be sent to them.

If subject does not respond within 24 hours, the research nurse will call the subject to check in and take answers over the phone.

CE-GAX001-01

V4.0

CR: 144

Weekly Check in with Subjects:

On day 7 and 14 subjects will be asked to complete the Dermatology Quality of life survey and questions on Ease of use, comfort, pain and confidence, at home. A link to the surveys will be emailed to them at 1pm in the afternoon with their daily check in.

Subjects will be required to respond by 5pm each evening. If subject has not responded by 5pm, a reminder text message will be sent to them.

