- Is it time consuming for a full dressing change
- How comfortable/uncomfortable is a dressing change
- Do you experience dressing related pain
- How confident are you that your dressing will not leak or move.

Once the dressing change is complete, please answer the following:

1. Is it easy/difficult to change your dressing using your current product and method? Please indicate the level of difficulty involved.

2. How time consuming is a dressing change using your current product and method?

Page 45 of 56

[figure not shown]
The Master Copy of this document is electronically approved and maintained as an electronic record

CE-GAX001-01 V4.0

CR: 144

[figure not shown]
3. How Comfortable is it to use and wear your current dressing?

4. Do you require pain killers before a dressing change? Please tick

Yes	No

5. Do you experience dressing related pain using current product?

[figure not shown]

CE-GAX001-01

[figure not shown]
V4.0

CR: 144

6. How confident are you that your current dressing will not leak or move?

7. How confident do you feel in yourself about your body image – self confidence/self esteem?

CE-GAX001-01

V4.0

CR: 144

22 APPENDIX 4 – SUBJECT ASSESSMENT FORM DAY 21

[figure not shown]
Please dress your wound using HidraWear AX

While you are dressing your wound, please pay close attention to the following:

[figure not shown]
- How easy/difficult it is
- Is it time consuming for a full dressing change
- How comfortable/uncomfortable is a dressing change
- Do you experience dressing related pain
- How confident are you that your dressing will not leak or move.

Once the dressing change is complete, please answer the following:

8. Is it easy/difficult to change your dressing using HidraWear AX? Please indicate the level of difficulty involved.

9. How time consuming is a dressing change using HidraWear AX?

Page 48 of 56

The Master Copy of this document is electronically approved and maintained as an electronic record

[figure not shown]

CE-GAX001-01

V4.0

CR: 144

[figure not shown]
10. How Comfortable is it to use and wear HidraWear AX?

11. Do you require pain killers before a dressing change? Please tick

Yes	No		

12.
Do you experience dressing related pain using HidraWear AX?

[figure not shown]

CE-GAX001-01

[figure not shown]
V4.0

CR: 144

13. How confident are you that HidaWear AX will not leak or move?

14. How confident do you feel in yourself about your body image – self confidence/self esteem?

CE-GAX001-01

V4.0

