25 APPENDIX 7 – SUBJECT CHECK INS

Daily Check in with Subjects:

Each day, at 1pm, subjects will receive an email requesting them to check in with the researcher by answering 3 questions.

- 1. What is your temperature?
- 2. How many dressings did you use in the last 24 hours?
- 3. Any comments?

This check in should take less than 5 minutes to complete.

Subjects will be required to respond by 5pm each evening. If subject has not responded by 5pm, a reminder text message will be sent to them.

If subject does not respond within 24 hours, the research nurse will call the subject to check in and take answers over the phone.

Weekly Check in with Subjects:

On day 7 and 14 subjects will be asked to complete the Dermatology Quality of life survey and questions on Ease of use, comfort, pain and confidence, at home. A link to the surveys will be emailed to them at 1pm in the afternoon with their daily check in.

Subjects will be required to respond by 5pm each evening. If subject has not responded by 5pm, a reminder text message will be sent to them.

If subject does not respond within 24 hours, the research nurse will call the subject to check in and take answers over the phone.

CE-GAX001-01

V4.0

CR: 144

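### The medication-free hour in Section 4.6 covers only the fever recheck, not the daily home reading that triggers it, and the check-in does not ask about painkillers, so a masked fever could be recognised late

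*Combined protocol and SAP*

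**What the plan says.** Section 4.6 sets up temperature monitoring in two steps. The first is a routine self-reading: "Subjects will be asked to measure and record their temperature daily and to contact nurse support if there is an elevation in temperature". The second applies once a subject has recorded more than 38 degrees. She contacts the research team, and then: "Subject will be asked to recheck temperature following 1 hour without temperature reducing medication (paracetamol ibuprofen et". If the fever persists she is sent to her GP and stops using the device.

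The home readings are reported through the daily check-in of 6.1.4 and Appendix 7: "Each day, at 1pm, subjects will receive an email requesting them to check in with the researcher by answering 3 questions". The first question is "What is your temperature". The other two ask for the number of dressings used in the past 24 hours and for any comments. Neither the check-in nor the schedules (6.4.1, Appendix 1) has an item for medication or for the time of the reading.

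The supplied-dressing risk table in 4.1.1 lists temperature against septicaemia, which it rates 5 for level and 1 for likelihood: "Monitor temperature twice daily during pilot period". That frequency differs from the daily reading in 4.6, but it has no medication condition either. Section 2.5 includes temperature recording among the topics on which the nurse trains subjects, without giving the content.

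On painkillers, Section 3.3 says of people with this disease: "Many subjects live with chronic pain, become sedentary, obese and have a high risk of developing anxiety and depression". The Day 0 and Day 21 subject forms (Appendices 3 and 4) ask: "Do you require pain killers before a dressing change? Please tick".

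**The concern.** By asking for a medication-free hour before the recheck, the sponsor accepts that paracetamol and ibuprofen can make a temperature reading unreliable. The recheck, however, happens only after a raised reading has been recorded. The precaution therefore protects fevers that have already been seen and does nothing for a fever that a dose has brought down to a normal-looking value. Nobody reading the check-in could tell whether a normal value followed a dose.

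What is at stake is prompt recognition of infection at home. In the supplied-dressing table, temperature is the only monitoring measure set against the most severe risk listed, although that risk is also rated least likely. A falsely normal reading may also reassure the subject.

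**Working it through.** This is mainly a comparison of texts. The only figure to reproduce is the length of the home period.

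**Home days.** Section 6.3.8 gives 22 days of participation, 2 of them visits: 22 − 2 = 20, as stated. The schedule in 6.4.1 agrees: Days 1–6, 7, 8–13, 14 and 15–20 give 6 + 1 + 6 + 1 + 6 = 20.

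**Where the plan deals with antipyretics.**

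| Step | Where | Medication condition or question |
|---|---|---|
| Routine reading | 4.6, risk table in 4.1.1 | None |
| Thermometer training | 2.5 | None stated; content not given |
| Daily check-in | 6.1.4, Appendix 7 | None; free-text comment only |
| Schedules | 6.4.1, Appendix 1 | None |
| Concomitant treatments | 4.5 | Antipyretics not addressed |
| Day 0 and Day 21 forms | Appendices 3, 4 | Painkillers before a dressing change; not linked to the reading, and outside the 20 home days |
| Recheck after more than 38 degrees | 4.6 | One hour without antipyretics |

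**Which readings escape.** There are three cases for a subject with a fever who has taken a dose.

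1. The reading is still above 38 degrees: the recheck starts.
2. The reading is lower but still raised: the instruction to contact nurse support for any elevation applies.
3. The reading looks normal: nothing in the temperature pathway starts.

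Only case 3 is a gap.

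**Delay or miss.** For a fever lasting k readings to be missed by temperature altogether, the first reading and every later one must be masked. A complete miss can therefore be no more likely than a masked first reading, whatever the masking probability. As an illustration only, assume that each reading is masked independently with probability m, and take k = 3 daily readings. The chance that all are masked is m³:

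- m = 0.10: 0.1%
- m = 0.25: 1.6%
- m = 0.50: 12.5%
- m = 0.75: 42%

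None of these values of m comes from the documents, and independence is doubtful for a regular painkiller user. The illustration supports the ordering, delay before miss, and nothing more.

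**The case against.** The best reply is that the two readings do different jobs. The routine reading is a screen. The recheck confirms that a fever persists untreated before the subject is referred and the device stopped. A condition on the confirming step does not oblige the plan to put one on the screen. That is right: a reader might infer that Section 4.6 contradicts itself, and it does not. What remains is a practical gap in the screen.

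The second reply is that safety does not hang on the thermometer, and much of this stands:

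- The schedules mark adverse events in every column from Day 0 to Day 21.
- Section 4.3 tells subjects to stop using the device and contact the nurse for any adverse effect, and names infection as a possible one.
- Section 6.3.4 suspends garment use for infection even without fever.
- The garment risk table, against fibre contamination, has: "Users instructed to carry out daily visual inspection of wound".
- Section 2.4 advises consulting a doctor or nurse for unexpected discomfort or wound irritation.
- Section 15.2 gives access to the nurse at any time.
- There are check-up calls on Days 7 and 14, and GP care continues (6.4.3).

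A reader might infer that a masked fever leaves the subject using the device with no route to stopping. The documents do not support that. Still, none of these measures shows that a normal reading followed a dose, and several rely on the subject noticing that something is wrong.

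Third, foreseeability is inferred. Section 3.3 describes pain, not drug use, and the Day 0 and Day 21 question does not say which drugs, how often or when. This is fair. It makes painkiller use plausible but does not measure it.

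Fourth, the training content, the instructions for use and the pyrexia process-flow figure are not shown. Any of them might already say to take the reading before a dose. This cannot be ruled out, although the figure's title places it after a reading above 38 degrees.

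**Conclusion.** The point holds as a small gap in safety monitoring. On the 20 home days, a fever suppressed to a normal-looking value would not start the temperature-triggered recheck and GP referral, and the check-in as written would not reveal why. The consequence is possible delay in recognising infection; a complete miss is less likely.

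The size cannot be given as a rate, because the documents report neither painkiller use nor how often a dose would fully suppress a fever. Two tempting figures should not be used as measures of harm. The first is 23 × 20 = 460 planned home readings (920 at the twice-daily rate), which counts readings without medication information, not masked fevers. The second is the seven days between scheduled contacts (Days 0, 7, 14 and 21). As a delay it would require every reading in between to be masked and every other safeguard to fail. The Day 7 and 14 calls also name no caller, so they cannot be assumed to be nurse assessments.

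The conclusion rests on painkiller use being plausible in this population and on the unseen training material, instructions for use and figure not already covering the point. No endpoint, sample size or analysis is affected. The sponsor could make this change; the study does not depend on it.

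**What to change.** 1. In Section 4.6 and the thermometer training of Section 2.5, tell subjects to take the daily reading before any dose of paracetamol, ibuprofen or a similar painkiller.
2. Add one item to the daily check-in (6.1.4 and Appendix 7): *Did you take paracetamol, ibuprofen or another painkiller before this reading, and if so when?*
3. If the answer is yes, the subject repeats the reading just before her next dose, and contacts the nurse if it is raised or if she feels unwell.

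The cost is a sentence in training that is already planned and one question on a check-in meant to take under 5 minutes. The downside is slight extra burden and some repeat readings, more of them for subjects who use painkillers often.

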6.3.4 Criteria for Withdrawal or Discontinuation

Subjects may withdraw from the study at any time without any rationale and without compromising their future medical care.

The subject may also be removed from the study by their physician or the consultant if they feel it is the best interest of the subject.

The use of the Hidrawear garment will be suspended if the patient presents with pyrexia and/or infection.

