15.4 Serious Adverse Event

A Serious Adverse Event (SAE) is any event (whether or not associated with the investigational device) that:

- Results in death
- Leads to serious deterioration in the health of the subject, that either resulted in
- Life threatening illness or injury, or
- Permanent impairment of a body structure or a body function, or
- In-subject or prolonged hospitalization, or
- Medical or surgical intervention to prevent life threatening illness or injury or permanent impairment to a body structure or body function.
- Leads to foetal distress, foetal death or a congenital abnormality or birth defect

CE-GAX001-01

V4.0

CR: 144

This includes device deficiencies that might have led to a serious adverse event if a) suitable action had not been taken or b) intervention had not been made or, c) if the circumstances had been less fortunate. These are handled under the SAE reporting system.

Planned hospitalisation for a pre-existing condition, without serious deterioration in health, is not considered a serious adverse event.

Subjects who experience and adverse will be released to their primary care provider/GP and excluded from the study.

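### The twice-daily temperature control for septicemia in 4.1.1 is not carried into the procedure, which collects one reading a day; secondarily, the visible fever text of 4.6 should be aligned with 6.3.4

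*Combined protocol and SAP*

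**What the plan says.** **Temperature frequency.** The risk table in 4.1.1 for the dressing supplied during the study has a row for septicemia caused by misuse of dressings, rated 5 for level of risk and 1 for likelihood. Its controls include "Monitor temperature twice daily during pilot period". The other two controls are following the user instructions and discontinuing use.

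Section 4.6 sets the task for subjects: "Subjects will be asked to measure and record their temperature daily and to contact nurse support if there is an elevation in temperature". Section 6.1.4 describes how the value is collected: "Each day, at 1pm, subjects will receive an email requesting them to check in with the researcher by answering 3 questions". The first of the three questions, repeated in Appendix 7, is "What is your temperature". The schedules in 6.4.1 and Appendix 1 mark a temperature record in every column from Day 0 to Day 21 and give no frequency within the day.

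**Device use on fever.** Under 4.6, a subject with a reading above 38 degrees contacts the research team and rechecks after 1 hour without antipyretics. It continues: "If pyrexia persists, subject will be directed to attend GP for immediate follow up and the use of the study device will be stopped". Section 6.3.4 says: "The use of the Hidrawear garment will be suspended if the patient presents with pyrexia and/or infection". Section 4.3 adds: "In all instances of adverse effects, subjects must cease using the device immediately and make contact with research nurse for further instruction". Section 4.6 also contains a process flow for pyrexia above 38 degrees, but that figure is not shown in the text available for review.

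**The concern.** A control written into a risk analysis works only if the procedure carries it out. Here the risk table names two temperature readings a day, while the sections that tell subjects and the research nurse what to do ask for a daily temperature and collect one value. Someone working from 4.6, 6.1.4 and Appendix 7 would have no prompt for the second reading and nowhere to record it. The hazard is rated at the highest level of the table's 1-to-5 scale. It also has the lowest likelihood rating, and both ratings belong in any account of what is at stake.

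The secondary issue is that two sections describe the device action on fever with different triggers. In the visible text of 4.6 the instruction to stop depends on fever persisting at the recheck. In 6.3.4 the instruction to suspend depends on pyrexia or infection alone. Unless the figure says otherwise, a reader who turns only to the text of 4.6 would not see that 6.3.4 already calls for suspension.

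**Working it through.** The plan states no count of temperature readings, so there is no figure of its own to reproduce. The check is a comparison of the text and one count.

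**1. Readings per subject**

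Inputs:
- Days on which the check-in runs: Days 1 to 21 (6.1.4), so 21 days.
- Readings a day under the risk control: 2 (4.1.1).
- Values collected a day by the check-in: 1 (one email and one temperature question, 6.1.4 and Appendix 7).

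Formula: readings = readings per day × days.
- Implied by 4.1.1: 2 × 21 = 42.
- Collected by the check-in: 1 × 21 = 21.
- Shortfall: 42 − 21 = 21, and 21 / 42 = 50%.

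Day 0 is left out because the check-in and daily use of the garment begin on Day 1.

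**2. Where each section stands on frequency**

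| Section | Frequency |
|---|---|
| 4.1.1, septicemia row | Twice daily |
| 4.6 | Daily, with no number of readings |
| 6.1.4 and Appendix 7 | One value at one check-in a day |
| 6.4.1 and Appendix 1 | Marked each day, no frequency |

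Only 4.1.1 names a second reading. No section in the visible text asks the subject to report it.

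**3. Device action on fever**

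| Section | Trigger | Action |
|---|---|---|
| 4.6, visible text | Above 38 degrees, still present at the 1-hour recheck | Stop, attend GP |
| 6.3.4 | Pyrexia and/or infection; no threshold or recheck stated | Suspend |
| 4.3 | Any adverse effect | Cease at once, contact nurse |

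A temporary suspension at the first reading (6.3.4), followed by a stop if fever persists (4.6), satisfies both rules. Section 4.3 leans the same way as 6.3.4, but it concerns adverse effects and not a temperature reading as such, so it does not settle the question. No visible sentence in 4.6 or 6.3.4 states the sequence or refers to the other section.

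The documents give no fever rate, so the number of subjects to whom the device rule would apply cannot be estimated.

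**The case against.** **On frequency.** Section 4.6 does not say once daily. A subject could measure twice and report once, and the duty to contact the nurse about a raised temperature does not depend on the check-in. This stands as a limit on the claim. The count of 21 describes what is collected; it does not show that subjects would measure only once. It does not remove the mismatch, because no visible step asks for the second reading or records it. It is also fair to say that the septicemia row has two other controls and the lowest likelihood rating, so the row does not rest on temperature alone.

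**On device use.** The strongest reply is that suspending and stopping are different acts that can follow one another, and that the fever pathway is drawn in a figure not shown here. The revision history records that version 3.0 expanded the process flow in 4.6 for this very event. The reply largely succeeds. A reader might infer that 4.6 and 6.3.4 contradict each other, or that the plan has no rule for the first hour or for resuming use after a fever settles. The documents do not support either inference: the rules are compatible in sequence, and silence in the text cannot be counted against the plan when the figure may supply the content. What remains is that the visible wording of the two sections is not aligned.

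**Conclusion.** The frequency mismatch holds and does not depend on the missing figure. Section 4.1.1 implies 42 readings per subject over Days 1 to 21, and the visible procedure collects 21, or half. This rests on taking the daily check-in as the collection step, which is how 6.1.4 and Appendix 7 describe it.

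The device-use point holds only as a secondary request to align the text of 4.6 with 6.3.4, subject to what the figure shows.

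Both are minor. They concern patient-safety wording. A reader might suppose that such a point bears on the results, but nothing in it touches the primary endpoint, the sample size or the primary analysis.

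**What to change.** **Main change.** State in 4.6 that temperature is measured twice daily, and have the daily check-in in 6.1.4 and Appendix 7 ask for both readings. The cost is a wording amendment and one more self-reading a day, or 21 per subject over Days 1 to 21. No extra visits or staff are needed, because the existing check-in carries both values.

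**Secondary change.** Add to 4.6 that garment use is suspended at the first reading above 38 degrees pending the 1-hour recheck, and refer to 4.6 from 6.3.4. Check the new sentence against the process-flow figure first; if the figure already says this, the text need only match it. The investigator and sponsor should confirm the threshold, since 6.3.4 gives none. This costs one sentence and one cross-reference.
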